7.4. Prior and Concomitant Medications/Treatments

Prior medications/treatments are defined as all medications/treatments taken/received within ten days (whether continuing or not) prior to Day 0. Particular attention should be made to identify the use of anti-coagulation or anti-platelet agents (e.g. acetylsalicylic acid).

Concomitant medications/treatments is defined as all medication taken/received from Day 0 (including medication taken immediately pre-injection and post-injection) until the last visit.

This document is confidential.

Medications missing both start and stop dates, or having a start date prior to the first dose of study product and missing the stop date, or having a stop date on or after the last dose of study product and missing start date will be counted as concomitant.

For partial dates, the following approach will be taken:

- If the start day is missing but the start month and year are complete, a medication will be excluded as being concomitant only if the start month/year is before the month/year of study product administration and if the stop date (either full date, month and year if missing day, or year if missing month and day) is before study product administration.
- If the start day and month are missing but the start year is complete, a medication will be excluded as concomitant only if the start year is before the year of study product administration and if the stop date (either: full date, month and year if missing day, or year if missing month and day) is before study product administration.

Prior and concomitant medications will be coded using the WHO Drug Dictionary, and subject incidence will be tabulated by Anatomic Therapeutic Class (ATC) Level 2 and preferred term (PT) for FAS by groups (i.e., Group A, Group B and the repeat-treatment subgroup), and be listed for subjects in the SAF. Subjects will be counted only once for each ATC or PT in the event that they have multiple records of the same ATC or PT in the database.

This document is confidential.

8. Effectiveness

The FAS and the PPS will be both considered equally important for the primary analysis. The primary effectiveness analysis will be performed with the FAS; if Princess® FILLER Lidocaine can be considered non-inferior to Juvéderm® Ultra XC according to this analysis, the results of the non-inferiority comparison based on the PPS can be considered confirmatory. Otherwise, the results of this analysis has to be considered exploratory. Overall non-inferiority is demonstrated only if the results are consistent for both analysis data sets. All secondary and additional effectiveness analyses will be conducted for the FAS and PPS.

A hierarchical testing procedure will be applied for the analysis of the primary outcome measure, as well as the key secondary outcome measures, in order to control multiplicity. At this, the following order will be used:

1. Analysis of primary effectiveness based on FAS
2. Analysis of primary effectiveness based on PPS
3. Analysis of key secondary effectiveness # 1 based on FAS
4. Analysis of key secondary effectiveness # 1 based on PPS
5. Analysis of key secondary effectiveness # 2 based on FAS
6. Analysis of key secondary effectiveness # 2 based on PPS

All statistical presentation will be done by treatment group (Princess® FILLER Lidocaine and Juvéderm® Ultra XC). For the primary analysis of the estimands of the primary effectiveness and of key secondary effectiveness endpoints, missing Week 24 assessments of NFL-SRS will be imputed by single imputation as no response. As sensitivity analyses, a best-case analysis (missing values for Princess® FILLER Lidocaine will be considered as a response, missing values for Juvéderm® Ultra XC will be considered as a non-response), a worst-case analysis (missing values for Princess® FILLER Lidocaine will be considered as a non-response, missing values for Juvéderm® Ultra XC will be considered as a response) will be performed on the FAS. Additionally, a tipping point analysis will be conducted on FAS to investigate the robustness of the results, and a complete-case analysis (includes subjects without any missing data) will be performed as supportive analysis.

For qualitative variables the frequencies (absolute and relative) will be calculated and compared between the treatment groups. Quantitative parameters will be summarized by mean value, standard deviation, minimum, first quartile, median, third quartile, and maximum per treatment group. In addition to this, mean value (incl. two-sided 95% confidence interval), standard deviation, minimum, first quartile, median, third quartile, and maximum will also be provided for the difference in quantitative parameters between the two treatment sides of a subject. The key secondary outcome measures 1 and 2 will be analyzed as described for the primary effectiveness outcome measure. Kappa statistics will be calculated in order to assess inter-rater consistency among the three independent blinded photographic reviewers.

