2.5. Brief Description

This is a randomized, subject- and evaluating investigator-blinded, controlled, multicenter, split-face comparison clinical investigation of Princess® FILLER Lidocaine compared to Juvéderm® Ultra XC in the treatment of moderate to severe NLFs.

Eligible subjects will be randomized at Baseline (Visit 2/Day 0) in a 1:1 ratio to Group A or Group B and will receive an injection of Princess® FILLER Lidocaine and an injection of Juvéderm® Ultra XC as follows:

Group A:

- Princess® FILLER Lidocaine on left NLF
- Juvéderm® Ultra XC on right NLF

Group B:

- Juvéderm® Ultra XC on left NLF
- Princess® FILLER Lidocaine on right NLF

The left NLF will be treated first and the right NLF thereafter.

The initial treatment will be administered at Baseline (Visit 2/Day 0) after randomization.

A touch-up treatment may be done at Visit 3a (Week 2) if an optimal aesthetic correction has not been achieved after initial treatment, as evaluated by the treating investigator. A touch-up treatment will be performed using the same type of device as initially applied.

A repeat-treatment may be done at Visit 6 (Week 36) or Visit 7 (Week 48) or Visit 7c (post repeat-treatment hold follow-up visit), if in the opinion of the treating investigator, the subject has returned to sufficient severity of NLFs that would have qualified them for enrollment into the clinical investigation initially. A repeat-treatment will be performed with Princess® FILLER Lidocaine on both NLFs.

Repeat-treatment:

Subjects who received repeat-treatment at Visit 6 (Week 36) or Visit 7 (Week 48) or Visit 7c (post repeat-treatment hold follow-up visit) will be included in the repeat-treatment subgroup, and the demographic, other baseline characteristics, medication, and applicable safety data will be analyzed by Group A, Group B, and repeat-treatment subgroup.

Subjects who received a repeat-treatment at Visit 6 (Week 36) will come back for safety follow-up visits at Visit 8a (Week 40) and at Visit 9a (Week 48). For these subjects, Visit 9a will be their end of study visit. Subjects who received a repeat-treatment at Visit 7 (Week 48) will come back for safety follow-up visits at Visit 8b (Week 52) and at Visit 9b (Week 60). For these subjects, Visit 9b will be their end of study

This document is confidential.

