6.2. Key Definitions

The study day is the day relative to the date of first administration of Investigational Medical Device (IMD), where Day 1 is the day of first administration of IMD.

The first dose date is defined as the first non-missing date where an administration of IMD was recorded. The last dose date is defined as the last non-missing date where an administration of IMD was recorded.

For on-treatment events (on or after first dosing day), Study Day = Event Date - date of first administration of IMD + 1; and for pre-treatment events (prior to first dosing day), Study Day = Event Date - administration of IMD.

Unless otherwise specified, baseline is the last non-missing observation before the administration of IMD, which is expected to be Day 1, or Screening if the Day 1 data are not available.

This document is confidential.

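### SAP 7.4 tests a medication with no start date against the last injection instead of the first, so some records that meet its own Day 0 definition are not captured as concomitant

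*SAP*

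**What the plan says.** SAP 7.4 opens with a general definition: "Concomitant medications/treatments is defined as all medication taken/received from Day 0", continuing to the last visit. One sentence on absent dates follows, naming three kinds of record that count as concomitant:

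- both dates absent: "Medications missing both start and stop dates";
- known start, absent stop: "having a start date prior to the first dose of study product and missing the stop date";
- absent start, known stop: "or having a stop date on or after the last dose of study product and missing start date will be counted as concomitant".

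Two bullets then cover partial start dates. Where month and year are known, "a medication will be excluded as being concomitant only if the start month/year is before the month/year of study product administration" and the stop date is also before administration. The bullet for a known year alone works the same way. Neither bullet says whether the first or the last administration is meant.

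SAP 6.2 keeps the two anchors apart: "The first dose date is defined as the first non-missing date where an administration of IMD was recorded", and "The last dose date is defined as the last non-missing date where an administration of IMD was recorded". Under SAP 2.5 a subject may have an optional touch-up at Week 2 and an optional repeat-treatment at Week 36, Week 48 or Visit 7c. SAP 7.4 tabulates medications in the FAS for Group A, Group B and the repeat-treatment subgroup, and lists them for the SAF.

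**The concern.** A medication with an unknown start and a known stop on or after Day 0 was necessarily in use on or after Day 0. It meets the general definition with no imputation. The missing-start clause asks for more: the stop must fall on or after the last injection. In a retreated subject that can be many months after Day 0.

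A programmer who takes the missing-date sentence as the complete rule would leave such a record out of the concomitant medication table. The omission would not be even across the table. It cannot occur when first and last dose coincide, and its window is long only after repeat-treatment. What is at stake is the accuracy of that table, chiefly its repeat-treatment column, and agreement between the SAP's definition and its programming rule.

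**Working it through.** The plan states no figure to reproduce here. The check compares the clause with the definition and then measures the gap.

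**Step 1: the rules side by side.** For a record with no start date and stop day *s*, counting the initial treatment as Day 0 (SAP 2.5 and 7.4):

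- Definition (SAP 7.4): concomitant if *s* ≥ first dose day = 0.
- Missing-start clause (SAP 7.4 with 6.2): counted if *s* ≥ last dose day *L*.
- Uncovered stop days: 0 ≤ *s* ≤ *L* − 1, which is *L* days.

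**Step 2: the last dose day *L*.** Week 2, 36 and 48 come from SAP 2.5. Visit 7c has no visit window (Protocol 7.1), so its latest timing is an assumption: maximum participation of 104 weeks (Protocol 9.4) less the 12 weeks from Visit 7c to Visit 9c, or 104 − 12 = 92 weeks.

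| Dosing history | *L* (nominal) | Uncovered stop days | Span |
|---|---|---|---|
| Initial treatment only | 0 | none | 0 |
| Touch-up, no repeat | 2 × 7 = 14 | 0 to 13 | 2 weeks |
| Repeat at Visit 6 | 36 × 7 = 252 | 0 to 251 | 36 weeks |
| Repeat at Visit 7 | 48 × 7 = 336 | 0 to 335 | 48 weeks |
| Repeat at Visit 7c, latest (assumed) | 92 × 7 = 644 | 0 to 643 | about 92 weeks |

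**Step 3: which records are exposed.**

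- Complete dates: decided by the general definition, so not exposed.
- Both dates missing: counted, so not exposed.
- Start before the first dose and no stop date: counted, so not exposed.
- Partial start date: excluded only if start and stop both precede administration. Not exposed if that means the first administration; the SAP does not say.
- Start date fully missing and stop date known, between Day 0 and the day before the last dose: not captured by the clause.

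Only the last kind is affected by the wording of the clause.

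**Step 4: is the last-dose anchor deliberate?** Three comparisons suggest not.

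- The mirror clause in the same sentence, for a missing stop date, uses the first dose.
- A drug with neither date is counted, while one known to have stopped at Week 10 in a subject later retreated is not captured. The record with better evidence of use after Day 0 gets less coverage.
- SAP 9.3 handles the parallel adverse-event case the inclusive way: with no start date at all, the event counts as treatment-emergent unless it had stopped before product administration.

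**Step 5: with the clause anchored on the first dose.** The condition becomes *s* ≥ 0, identical to the definition. The gap is 0 days for every row of the table.

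**The case against.** The strongest reply is that the sentence lists sufficient conditions. It does not say that other records are excluded, and SAP 7.4 words exclusion explicitly in the partial-date bullets when it intends it. A stop date after Day 0 already satisfies the general definition, so a careful programmer would count the record. This stands in part: the text contains no express exclusion. It does not remove the problem. A stop on or after the last dose would satisfy the general definition too, so the clause has work to do only as the operational rule, and as such its anchor is wrong.

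A reader might go further and infer that medications taken between Day 0 and the repeat-treatment drop out of the table in general. The documents do not support that, because every kind of record in Step 3 except the last is handled elsewhere or counted.

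A reader might also infer that long-term antiplatelet or anticoagulant use is hidden and that comparisons of bruising suffer. That does not follow either. An ongoing drug with no stop date is counted. Use from ten days before to three days after injection is prohibited (Protocol 8.4.2) and an exclusion criterion (Protocol 9.1.2), and SAP 4.5 sends enrollment-criteria and prohibited-treatment deviations to blinded review, independently of this table. In a split-face design the same subject receives both devices at the initial treatment, so a systemic drug acts on both sides. No planned model or test uses concomitant medication.

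Finally, Protocol 11 calls for full source data verification and Protocol 15.2 for completeness checks with queries. These should make fully missing start dates less common, though not impossible.

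**Conclusion.** The point holds as a wording error with minor consequences. The missing-start clause conflicts with the SAP's Day 0 definition and with its own mirror clause. Read literally as the full rule, it fails to capture records with no start date and a known stop between Day 0 and the last dose.

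The spans in the table are the width of the window in which a stop date goes uncovered, not an estimate of how many records are lost. That number cannot be obtained from the documents. The spans use nominal visit days, and the Visit 7c figure rests on the 104-week assumption. Any undercount would sit mainly in the repeat-treatment subgroup of a descriptive FAS table. The records still appear in the SAF listing of prior and concomitant medications (Listing 16.2.4.3). The primary and key secondary analyses and the device comparison of injection site reactions are unaffected.

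**What to change.** In the third limb of the missing-date sentence in SAP 7.4, replace last with first, so that a medication with no start date counts as concomitant when it stopped on or after the first dose of study product. In the two partial-date bullets, state that the administration referred to is the first one; otherwise the same question of anchor remains open there.

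The cost is one word and one short clarification in the SAP, plus a check that the program deriving the concomitant flag follows them. No new data are needed and no other analysis changes.

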8.1. Evaluation Methods and Response Rate

8.1.1. Nasolabial Folds (NLF) Severity Rating Scale (NLF-SRS)

NLF-SRS is a five-point scale graded from 0 (None/minimal: No visible wrinkles) to 4 (Extreme: Extremely deep and long fold with skin redundancy) see [Table 3](#). After enrollment, live assessments

This document is confidential.

using the NLF-SRS, will be performed by the treating investigator and the independent blinded evaluating investigator in conjunction at Baseline and as separate assessments at Week 12 (Visit 4), at Week 24 (Visit 5), at Week 36 (Visit 6), at Week 48 (Visit 7) and the post repeat-treatment hold follow-up visit (Visit 7c). Photographic assessments using the NLF-SRS will be performed at the end of the clinical investigation by three blinded independent photographic reviewers. The left and the right NLF will be graded separately.

Table 3 NLF Severity Rating Scale (NLF-SRS)

NLF-SRS grade	Definition
0	None/minimal: No visible/minimal nasolabial folds
1	Mild: shallow but visible nasolabial fold with a slight indentation
2	Moderate: moderately deep nasolabial fold
3	Severe: very deep nasolabial fold with prominent facial feature
4	Extreme: Extremely deep and long nasolabial fold with skin redundancy

8.1.2. Global Aesthetic Improvement Scale (GAIS)

The GAIS is a five-point scale that rates global aesthetic improvement from the pre-treatment appearance (Narins et al., 2003). The scale is presented in [Table 4](#).

The GAIS assessment will be performed separately by the independent blinded evaluating investigator and the subject at Week 12 (Visit 4), at Week 24 (Visit 5), at Week 36 (Visit 6), at Week 48 (Visit 7), and the post repeat-treatment hold follow-up visit (Visit 7c). At Week 36, Week 48, and Visit 7c GAIS assessments will be performed prior to repeat-treatment. Separate assessments will be performed for the left and the right side of the face.

Table 4 Global Aesthetic Improvement Scale (GAIS)

Grade	Definition
1 Very much improved	Optimal aesthetic result for the implant in this subject.
2 Much improved	Marked improvement in appearance from initial condition, but not completely optimal for this subject. A touch-up would slightly improve the result.
3 Improved	Obvious improvement in appearance from the clinical condition, but a touch-up or retreatment is indicated.
4 No change	The appearance is essentially the same as the original condition.
5 Worse	The appearance is worse than the original condition.

Cited from (Narins et al., 2003)

8.1.3. Satisfaction with Outcome

FACE-Q Subject Satisfaction with Outcome Questionnaire, see [Appendix 2](#), will be used to measure subjects satisfaction with the results of their most recent procedure.

“FACE-Q Subject Satisfaction with Outcome” assessments will be performed by the subject at Week 12 (Visit 4), at Week 24 (Visit 5), at Week 36 (Visit 6), at Week 48 (Visit 7), and the post repeat-treatment hold follow-up visit (Visit 7c). Separate assessments will be performed for the left and the right side of the face.

This document is confidential.

Satisfaction with Outcome Conversion Table:

The FACE-Q Subject Satisfaction with Outcome Questionnaire consists of 6 questions with answers ranging from 1 – “Definitely disagree” over 2 – “Somewhat disagree” and 3 – “Somewhat agree” to 4 – “Definitely agree”. The sum score can thus range from 6 to 24.

Higher scores reflect a better outcome. If missing data is less than 50% of the scales items, that is if at least 3 questions out of 6 questions are answered, insert the mean score of the completed items to the missing items. If less than 3 questions are answered, no sum score will be calculated. Use the conversion table below to convert the raw scale summed score into a equivalent Rasch transformed score from 0 (worst) to 100 (best).

Raw scale summed score	Equivalent Rasch transformed score (0-100)
6	0
7	19
8	24
9	28
10	31
11	35
12	38
13	41
14	45
15	48
16	52
17	55
18	59
19	63
20	68
21	73
22	79
23	87
24	100

8.1.4. Appraisal of Nasolabial Folds

FACE-Q Subject Appearance Appraisal of Nasolabial Folds Questionnaire, see [Appendix 3](#), will be used to measure subjects appraisal of Nasolabial Folds with the results of their most recent procedure.

“FACE-Q Subject Appearance Appraisal of Nasolabial Folds” assessments will be performed by the subject at Week 12 (Visit 4), at Week 24 (Visit 5), at Week 36 (Visit 6), at Week 48 (Visit 7), the post repeat-treatment hold follow-up visit (Visit 7c). Separate assessments will be performed for the left and the right side of the face.

Appraisal of Nasolabial Folds Conversion Table:

The FACE-Q Subject Appearance Appraisal of Nasolabial Folds Questionnaire consists of 5 questions with answers ranging from 1 – “Not at all” over 2 – “A little” and 3 – “Moderately” to 4 – “Extremely”. The sum score can thus range from 5 to 20.

This document is confidential.

[figure not shown]
Ensure the data are rescored as follows: "Not at all" = 4; "A little" = 3; "Moderately" = 2; "Extremely" = 1. Higher scores reflect a better outcome. If missing data is less than 50% of the scales items, that is if at least 3 questions out of 5 questions are answered, insert the mean score of the completed items to the missing items. If less than 3 questions are answered, no sum score will be calculated. Use the conversion table below to convert the raw scale summed score into a equivalent Rasch transformed score from 0 (worst) to 100 (best).

Raw scale summed score	Equivalent Rasch transformed score (0-100)
5	0
6	10
7	18
8	24
9	30
10	36
11	42
12	47
13	52
14	58
15	63
16	69
17	76
18	83
19	91
20	100

8.1.5. Subject's Evaluation of Pain

The subject's perception of pain will be evaluated for treatments with Princess® FILLER Lidocaine and Juvéderm® Ultra XC. This evaluation will be assessed using a scale adapted from the 11-point Numeric Pain Rating Scale (NPRS), where "0" indicates "no pain" and "10" indicates "the worst pain imaginable".

The evaluation of subject's pain will be done starting 15 min (+/- 3 min) after last injection and at 15 min-intervals (+/- 3 min) for 60 min (+/- 3 min) post-treatment (initial and repeat treatments) using the adapted NPRS. Separate assessments will be performed for the left and the right side of the face and overall. Overall assessment will be used for summary, and left, right side and overall assessments will be listed.

8.1.6. Injection Volume

For each subject, the total volume injected will be recorded separately for each treatment (initial, touch-up and repeat-treatments).

8.1.7. Time to Repeat-Treatment

For each subject, the time from initial treatment to repeat-treatment will be recorded for each investigational group and assessed by tabulating the following rates:

This document is confidential.

- Repeat-treatment at Week 36
- Repeat-treatment at Week 48
- Repeat-treatment at Visit 7c
- No repeat-treatment

8.1.8. Clinical Photography

Clinical photography of the subjects face will be taken at Screening (Visit 1), on Day 0 (Baseline) and at Week 12, 24, 36, 48, and Visit 7c after initial treatment (at Visit 2, 4, 5, 6, 7 and Visit 7c, respectively) under standardized conditions in accordance with the manual. On treatment days (initial- and/or repeat-treatments), the clinical photography will be performed prior to the treatment.

8.1.9. Response Rate for NLF-SRS

The response rate for week X in treatment group A is defined as follows:

Response rate

$$= \frac{\text{Number of Responders at Week X with treatment A}}{\text{Number of Responders at Week X with treatment A} + \text{Number of Non-Responders at Week X with treatment A}}$$

The change from Baseline in NLF-SRS at Week X is calculated as follows (separately for the treatment groups):

$$= NLF - SRS_{\text{Week X}} - NLF - SRS_{\text{Baseline}}$$

'Responder' is defined as a subject with at least one grade improvement in NLF-SRS at Week X compare to Baseline.

Each subject's 'Response' for NLF-SRS will be assessed for both treatment groups, Princess® FILLER Lidocaine and Juvéderm® Ultra XC, in this split-face design.

